#### 9.4.3 Overall accrual

Accrual period 1 will open once at least 4-5 sites have all regulatory approvals completed and are ready to enroll participants immediately. The team estimates that these 4-5 sites should be able to accrue approximately 4-6 participants per month per site. As other sites begin accrual period 1, the team anticipates that accrual period 1 (n=60) should be completed within approximately 2-4 months.

Accrual period 2 will open once the accrual period 1 interim PK and safety analysis is completed. The team anticipates ultimately 15 sites each enrolling 4-5 participants per month. Thus, taking into account a slow, early accrual period, accrual period 2 (n=411) is anticipated to take approximately nine months.

Not accounting for the time during which accrual is suspended after the accrual period 1 closes and until the accrual period 1 interim PK and safety analysis is completed, the expected time to reach full accrual (n=471) is approximately 13 months.

### 9.5 Monitoring

#### 9.5.1 Monitoring During the Dose-Finding Period in Accrual Period 1 Participants

Since initiation of ART may be delayed for up to 7-14 days after starting anti-TB therapy to allow participants sufficient time to assess tolerability of TB medications, PK assessments will be timed based on initiation of ART. Until the final SMC review during the dose-finding period in accrual period 1 participants,

the core team will closely monitor adverse events (AEs) and drug concentrations. The protocol data manager will provide unblinded detailed AE summary reports to the core team on a weekly basis. These reports will be discussed on weekly core team calls.

### PK and Safety Criteria

- For RBT (Arms A and C), equivalence analyses will compare day  $12 \pm 2$  (after initiation of ART) RBT 24-hour AUC and  $C_{max}$  with control data derived from prior PK studies, as determined by whether the 90% confidence intervals of the ratios of the RBT concentrations (when co-administered with LPV/r) relative to daily RBT concentrations in the absence of LPV/r are fully contained within the pre-specified NEB of 67%-150%. RBT concentrations in Arms A and C will be judged acceptable if equivalence is declared according to these PK parameters.
- For LPV in Arm B, the primary PK parameter is the day  $12 \pm 2$  (after initiation of ART)  $C_{min}$  ( $C_{12}$ ), and the acceptable lower limit value is  $\geq 1$  mg/L. LPV concentrations in Arm B will be judged acceptable if no more than three participants have a  $C_{min} < 1$  mg/L.
- No more than three participants in any treatment arm experience a Grade 3 or Grade 4 AE attributable to study-provided medication by 28 days after ART initiation.
- No more than three participants in any treatment arm discontinue study-provided drug(s) for treatment-limiting toxicity or intolerance (such that PK assessments within the day  $12 \pm 2$  (after initiation of ART) window cannot be completed).

The justification behind the RBT PK criterion is given in section 9.4.1. The other three criteria depend on the number of events (i.e., no more than 3). Based on Table 9.2 below, supposing the underlying rate is 10%, with  $X=3$ , there is an 87% chance of the study regimen in a particular arm going forward to accrual period 2.

Table 9.2. Probability (%) of Deciding the Criterion is Acceptable Based on a Range of Underlying Rates

Underlying Rate	Probability of X or Fewer Events in 20 Participants Given the Underlying Toxicity Rate:				
	X=1	X=2	X=3	X=4	X=5
0.05	0.736	0.925	0.984	0.997	0.999
0.10	0.392	0.677	0.867	0.957	0.989
0.15	0.176	0.405	0.648	0.830	0.933
0.20	0.069	0.206	0.411	0.630	0.804
0.25	0.024	0.091	0.225	0.415	0.617

The core team will also examine the LPV concentrations in Arms A and C in order to determine if RBT affects LPV concentrations. Any dose modifications of

LPV in Arms A and C will be the guided by the modifications proposed for Arm B (see Table 5.1 in section 5.1.1).

While the intent is to conduct the accrual period 1 PK and safety interim analysis after 54-60 accrual period 1 participants have completed 28 days of ART, available drug concentrations and safety data will be assessed weekly by the core team in an unblinded fashion as follows. Sites will be asked to batch PK samples and ship them every two weeks to the ACTG repository with immediate re-shipping to the PK laboratory. The PK laboratory will measure drug concentrations as soon as possible after receipt of shipments and will report results within 2 weeks of receiving the samples. The core team will monitor all available concentrations weekly for those results received to date. An early interim analysis of PK results and safety criteria will be evaluated after the first 10-12 participants in each treatment arm complete 28 days of ART and the day  $12 \pm 2$  drug concentrations are available to assess any early trends suggesting lower or higher than expected concentrations of any study-provided drug(s). (Please see the Study Monitoring Plan for more details on how this early PK assessment will be completed.) If the early assessments indicate concentrations out of acceptable ranges for more than three participants in a treatment arm or trends related to safety concerns, an early ACTG Study Monitoring Committee (SMC) evaluation will be triggered. Any dose adjustments recommended by the SMC in consultation with the core team after this interim evaluation will be implemented for any new accrual period 1 participants enrolled as soon as possible after the review and for any already enrolled participants who have drug concentrations clearly out of acceptable ranges. However, the decision to revise dose schedules and treatment duration of participants with inadequate drug concentrations would be made based not just on the drug concentrations, but also on all available clinical data regarding TB and HIV endpoints. While true real-time reporting of drug concentrations will not be possible, individual participants identified, either during weekly core team monitoring or during any early SMC monitoring assessments, who have clearly inadequate concentrations of any study-provided drug would be reported to the sites as soon as that determination is made, and individual dose adjustments may be recommended according to the dose adjustment schedule in Table 5.1 in section 5.1.1. Accrual period 1 participants for whom early dose adjustments are recommended will have drug concentrations repeated  $12 \pm 2$  days after initiating the adjusted dose. If no early PK or safety trends are identified during core team or early SMC monitoring, dosing will continue in participants enrolled during accrual period 1 as per assigned treatment arm.

NOTE: Any participants determined to have clearly inadequate RBT concentrations during the accrual period 1 PK evaluation should be monitored closely after dose adjustments for TB outcomes throughout the course of their TB treatment.

After 54-60 accrual period 1 participants have completed 28 days of ART and have drug concentrations available, the core team, together with the SMC, will review the results of the full accrual period 1 interim PK and safety analysis.

If the acceptable PK criteria for RBT and LPV are met, and if three or fewer participants in each treatment arm report  $\geq$  Grade 3 AEs attributed to study-provided drug(s) by 28 days of ART, and if three or fewer participants in each treatment arm discontinue study-provided drug(s) for treatment-limiting toxicity or intolerance (such that PK assessments cannot be completed), then accrual period 2 will open at the planned dose schedules of LPV/r and RBT.

If acceptable PK criteria are not met, or if more than three participants in one or more treatment arms report  $\geq$  Grade 3 AEs attributed to study-provided drug(s) by 28 days of ART, or if more than three participants in one or more treatment arms discontinue study-provided drug(s) for treatment-limiting toxicity or intolerance (such that PK assessments cannot be completed), the SMC, in consultation with the core team, may elect to adjust the doses of RBT and/or LPV/r, as described above for all participants in the affected arm identified with inadequate study-provided drug concentrations. Repeat steady-state (day 12  $\pm$  2 after dose adjustment) drug concentrations will be obtained for only the study arm participants in whom a dose was adjusted. A second accrual period 1 PK and safety interim analysis will be conducted after all accrual period 1 participants undergoing dose adjustment have completed 28 days of dose-adjusted treatment and when day 12  $\pm$  2 post-dose adjustment levels are. This second analysis will include all accrual period 1 participants with available data.

The core team and SMC will then review the results of the second accrual period 1 interim PK and safety analysis. If acceptable PK criteria are not met, or if more than three participants in one or more treatment arms report  $\geq$  Grade 3 AEs attributed to study-provided drug(s) by 28 days of ART, or if more than three participants in one or more treatment arms discontinue study-provided drug(s) for treatment-limiting toxicity or intolerance (such that PK assessments cannot be completed), then a decision will be made about whether to continue, modify (e.g., add additional participants in the accrual period 1 to assure adequate PK assessment are completed), or halt the treatment arm(s) in question, based on analysis of the nature of the AEs and reasons for study-provided drug discontinuation, and the degree of PK criteria failure. At this second interim review, if three or fewer participants report  $\geq$  Grade 3 AEs attributed to study-provided drug(s), and if three or fewer participants discontinue study-provided drug(s) for treatment-limiting toxicity or intolerance (such that PK assessments cannot be completed), and if acceptable PK criteria are met for at least two of the treatment arms, the SMC, in consultation with the core team, will determine whether accrual period 2 will open.

If, based on the SMC's determination, unacceptable PK and/or safety criteria are met within two treatment arms, then further enrollment into the study may be stopped, and accrual period 1 participants will be managed according to best available local TB and ARV treatment. These participants will be followed off study drug for the remainder of study follow-up (up to 72 weeks).

If the SMC determines that accrual period 2 enrollment should proceed, accrual period 2 participants will then be randomized 1:1:1 to Arm A, B, or C (or with

equal probability to the remaining sample size in the remaining treatment arms) at the doses determined during the dose-finding period in accrual period 1 participants. No individual dose adjustments will be made based on drug concentrations for participants enrolled during the accrual period 2.

Based on this monitoring, if criteria are determined to be unacceptable in any treatment arm before the three accrual period 1 cohorts are fully enrolled, further accrual to the arm in question may be stopped.

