## SCHEMA

## A5290

A Randomized, Phase 2b Study of a Double-Dose Lopinavir/Ritonavir Based Antiretroviral Regimen with Rifampin-Based Tuberculosis Treatment versus a Standard-Dose Lopinavir/Ritonavir Based Antiretroviral Regimen with Rifabutin-Based Tuberculosis Treatment with or without Raltegravir in HIV-1-Infected Persons Requiring Treatment for Active TB and HIV

DESIGN

A5290 is a prospective, randomized (1:1:1), open-label, phase 2b study comparing three lopinavir/ritonavir (LPV/r)-based antiretroviral (ARV) regimens among participants in high tuberculosis (TB) endemic resource-constrained settings undergoing treatment for confirmed or probable TB and requiring protease inhibitor (PI)-based antiretroviral therapy (ART). A two accrual period design will be used, including a full pharmacokinetic (PK) and safety evaluation to be conducted when 54-60 participants enrolled during the accrual period 1 have completed 28 days of ARV treatment and day  $12 \pm 2$  (after initiation of ART) drug levels are available (an early interim PK and safety evaluation will also be completed when 10-12 participants per arm have completed 28 days of ARV treatment and day  $12 \pm 2$  drug levels are available).

DURATION

Each participant will be followed until week 72.

SAMPLE SIZE

471 participants.

POPULATION

HIV-infected persons (male or female) at least 18 years of age with documented HIV infection, a clinical diagnosis of probable or confirmed active TB (including extrapulmonary TB) with susceptibility to rifampin (RIF), and who require a PI-based ARV regimen.

REGIMENS

Study-provided drugs include lopinavir/ritonavir (LPV/r), ritonavir (RTV), raltegravir (RAL), and rifabutin (RBT).

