Use of an 800 mg/200 mg BID dose of LPV/r may also be easier to administer in resource-constrained settings because this dose takes advantage of the better tolerated and more stably stored Meltrex co-formulated tablets that do not require a separate prescription for extra doses of the additional RTV. This trial will evaluate the strategy of double-dose LPV/r in combination with RIF-based TB therapy using the now standard heat-stable Meltrex formulation of LPV/r. This regimen of double-dose LPV/r (800 mg/200 mg BID) is currently being used as standard of care in South Africa and other resource-constrained settings for patients being treated for active TB with a RIF-based regimen and who require ART containing a PI. A recent small PK study among stable participants on LPV/r-based ART showed that serum concentrations of LPV/r were dramatically decreased after the addition of RIF, but that doubling the dose of LPV/r restored trough concentrations of LPV/r. Two participants in the study had increased liver transaminases following the addition of RIF to LPV/r-based ART, but both participants did well with discontinuation of RIF. This strategy has not been evaluated in controlled clinical trial settings that evaluate both virologic and TB treatment outcomes, and there are very limited data about its tolerability and efficacy for patients with HIV-related TB.

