C	LPV 400 mg/RTV 100 mg tabs BID + two NRTIs + RAL 400 mg BID	INH 300 mg daily, RBT 300 mg daily, then 150 mg daily upon initiation of ART*, EMB (weight-based dose) daily, PZA (weight-based dose) daily, and pyridoxine 25 mg daily. EMB and PZA will be discontinued after 8 weeks of treatment; INH, RBT 150 mg daily (or the adjusted dose determined by PK), and pyridoxine will continue for a minimum total duration of 24 weeks. INH, RBT, and pyridoxine may continue beyond the 24 weeks to a maximum of 48 weeks at the discretion of the primary clinician; the protocol core team must be notified.	LPV/r + two NRTIs + RAL will continue at standard dosing through week 72	This regimen follows the same rationale as for Arm A but adds RAL in an attempt to enhance the antiviral activity of LPV/r when combined with RBT to evaluate whether this approach is associated with a better virologic response than the other two arms.

\*NOTE: In Arms A and C, RBT should be administered at a dose of 300 mg daily until the start of antiretroviral therapy at which time the dose should be reduced to the 150 mg daily dose. If LPV/r is stopped prematurely during TB treatment, the RBT dose should be increased to 300 mg daily and the team should be notified. All participants will receive TB treatment according to in-country TB guidelines for daily TB treatment and directly observed therapy (DOT), except that all study participants will receive daily TB treatment 7 days per week, i.e., participants will not use a 5 days per week schedule that may be recommended in some in-country TB programs.

Accrual will take place in two accrual periods. Accrual period 1 will enroll participants who will undergo an initial dose-finding period before continuing regular study follow-up through 72 weeks. Once review of the dose-finding data in accrual period 1 is completed, accrual period 2 will begin.

#### Accrual Period 1

Sixty participants will be randomized 1:1:1 (20 participants per arm) to one of three treatment arms as detailed above. Anti-TB therapy with study-provided RBT or non-study-provided RIF and non-study-provided INH, EMB, and PZA should be started within 72 hours of randomization. ART should be started as soon as possible after initiating anti-TB therapy, but may be delayed for up to 7-14 days after starting anti-TB therapy to allow participants sufficient time to assess tolerability of TB medications. Participants will then undergo a formal PK and safety evaluation to include:

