### 5.3 Pharmacy: Product Supply, Distribution, and Accountability

#### 5.3.1 Product Supply

Lopinavir/ritonavir and ritonavir will be supplied by Abbott Laboratories.

Raltegravir will be supplied by Merck & Co., Inc.

Rifabutin will be supplied by Pfizer Inc.

Lopinavir/ritonavir, ritonavir, raltegravir, and rifabutin will be made available through this study. Isoniazid, rifampin, ethambutol, pyrazinamide, pyridoxine and NRTI background will not be provided through the study and must be obtained by non-study prescription.

Fixed-dose combination TB treatment tablets will be permitted for this study only for participants randomized to Arm B. Fixed-dose combination tablets containing INH, RIF, EMB, and PZA may be used during the intensive phase of TB treatment and fixed-dose combination tablets containing INH and RIF may be used for the continuation phase of TB treatment.

Fixed-dose combination TB treatment tablets will not be permitted for participants randomized to Arms A or C.

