### 6.2.2 Randomization and Entry Evaluations

Entry evaluations will occur after randomization. Entry evaluations and initiation of anti-TB therapy with study provided RIF or RBT and non-study provided INH, EMB and PZA should be started within 72 hours of randomization. ART should be started as soon as possible after initiating anti-TB therapy, but may be delayed for up to 7-14 days after initiation of anti-TB therapy to allow participants sufficient time to assess tolerability of TB medications. Dates of initiation of all study provided and non-study provided anti-TB and ART medications will be entered into the ACTG database.

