### **1.5.2 Safety Criteria**

- 1) No more than three participants in any treatment arm experience a Grade 3 or Grade 4 AE “related to study-provided drug(s)” (as deemed by the TDM Team: DAIDS Clinical Representative, Protocol Co-Chairs, Protocol Vice Chair, Protocol Pharmacologist, Statisticians, Data Manager, Laboratory Data Manager, and Clinical Trials Specialist) by 28 days after initiation of study-provided ART and TB medications.
- 2) No more than three participants in any treatment arm discontinue study-provided drug(s) for treatment-limiting toxicity or intolerance (such that PK assessments within the day  $12 \pm 2$  [after initiation of study-provided ART and TB medications] window cannot be completed).

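### The period 1 safety criteria count rifabutin events in Arms A and C but not rifampin-only events in Arm B, so Arm B meets a looser test than if its rifamycin counted

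*Protocol*

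**What the plan says.** Protocol 9.5.1 sets two count-based safety criteria for each arm in accrual period 1: "No more than three participants in any treatment arm experience a Grade 3 or Grade 4 AE attributable to study-provided medication" (counted over the first 28 days of ART), and "No more than three participants in any treatment arm discontinue study-provided drug(s) for treatment-limiting toxicity or intolerance" where the day 12 PK assessment is lost as a result. Sections 3.0, 9.2.1.3, 9.2.1.4 and 9.6.1 carry the same restriction. SAP 1.5.2 repeats it, for example in the words "discontinue study-provided drug(s) for treatment-limiting toxicity or intolerance".

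The Schema defines the set: "Study-provided drugs include lopinavir/ritonavir (LPV/r), ritonavir (RTV), raltegravir (RAL), and rifabutin (RBT"). Section 11.4.2 names the same agents for expedited reporting. Section 5.3.1 adds: "Isoniazid, rifampin, ethambutol, pyrazinamide, pyridoxine and NRTI background will not be provided through the study". Sections 3.0 and 5.1.1 draw the line between the two rifamycins directly: "study-provided RBT or non-study-provided RIF and non-study-provided INH, EMB, and PZA".

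Two places disagree. Section 6.2.2 refers to "initiation of anti-TB therapy with study provided RIF or RBT", and section 7.2.5 also describes rifampin as study-provided.

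The SAP is not uniform on attribution. Section 1.5.2 counts events deemed related. Section 4.1, in the table tagged to the same criterion, counts related, probably related and possibly related events.

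**The concern.** Section 9.5.1 justifies the limit of three by the chance that the study regimen in an arm goes forward. In every arm the co-treatment under test is LPV/r with a rifamycin, with RAL added in Arm C. Arms A and C are scored on both LPV/r and the rifamycin. Arm B is scored on LPV/r only, because its rifamycin comes from local supply. Supply source thus helps decide what counts as toxicity.

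The events left out are foreseeable. Section 7.2.5 names rifampin, rifabutin and raltegravir as the likeliest causes of rash. Sections 7.2.1 and 7.2.2 list rifampin among the causes of raised transaminases and bilirubin. Section 2.1 describes two people whose transaminases rose after rifampin was added to LPV/r and reports that "both participants did well with discontinuation of RIF". A Grade 3 event attributed to rifabutin alone counts; the same event attributed to rifampin alone does not. Under the second criterion, stopping rifampin alone is not a discontinuation of a study-provided drug.

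Because the protocol contradicts itself on rifampin's status, two analysts could also reach different Arm B counts from the same data.

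**Working it through.** **Reproducing the plan's figure.** Table 9.2 gives the probability of X or fewer events in 20 participants. With X = 3 and rate p,

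P(pass) = sum over k = 0 to 3 of C(20,k) p^k (1−p)^(20−k).

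At p = 0.10 the terms are 0.1216 + 0.2702 + 0.2852 + 0.1901 = 0.867, the 87% quoted in section 9.5.1. The other X = 3 entries also reproduce: 0.984 at 5%, 0.648 at 15%, 0.411 at 20% and 0.225 at 25%. The table is correct, but it uses one generic rate and does not say which drugs' events make up that rate in each arm.

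**Inputs.** From the documents: 20 participants per arm and a limit of 3. Assumed, because the documents give no rates by causal drug:
- l, the proportion with an event attributed to LPV/r;
- r, the proportion with an event attributed to the rifamycin alone;
- independence of the two.

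**Counted rate.** If the rifamycin counts, the rate is q = 1 − (1−l)(1−r). If it does not, the rate is l.

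**Arm B, criterion 1, as written and with rifampin counted, l = 10%:**

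| r | q | P(pass) as written | P(pass) with rifampin counted |
|---|---|---|---|
| 2% | 1 − 0.90×0.98 = 11.8% | 0.867 | 0.796 |
| 5% | 1 − 0.90×0.95 = 14.5% | 0.867 | 0.672 |
| 10% | 1 − 0.90×0.90 = 19.0% | 0.867 | 0.456 |

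Over the same r of 2%, 5% and 10%, l = 5% gives 0.984 as written against 0.955, 0.876 and 0.672. With l = 20% it is 0.411 against 0.345, 0.257 and 0.147. The direction never changes; the size depends on r.

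**Arm B against Arm A.** Arm A's counted rate is q. Arm B's is its own double-dose LPV/r rate. They are equal when that rate reaches q: 9.75% if Arm A has l = r = 5%, 14.5% if Arm A has 5% and 10% (in either order), and 19% if l = r = 10%. Arm A then passes with probability 0.876, 0.672 and 0.456. If Arm B's LPV/r rate is 20%, it passes with 0.411, below Arm A in all three cases. The ranking of the arms can therefore go either way.

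**The case against.** A reader might infer that Arm B passes more easily than A or C. For example, take a true rate of 25% in every arm and let 40% of Arm B's events be rifampin-only. The counted rates are 25% and 25% × 0.6 = 15%, and Table 9.2 gives 0.225 for A or C and 0.648 for B. The documents do not support this. Section 9.4.2 expects adverse effects especially in the double-dose LPV/r arm, and those events count. The 40% share has no source. At a 10% share the counted rate is 22.5%, and P(pass) by the formula above is 0.31, close to 0.225.

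A second reading, that rifampin toxicity never counts, also goes too far. Under SAP 4.1 an Arm B event escapes only if it is judged not even possibly related to LPV/r, and section 7.2.1 says ARVs and several TB drugs can all disturb liver tests. For transaminases above the limit in that section all medications are held, so LPV/r is interrupted as well. Criterion 2 is narrow in any case, since it covers only stops that prevent the day 12 PK assessment. These points reduce the gap but do not close it: SAP 1.5.2 says only related, and neither rifampin-only events nor rifampin-only stops are brought back.

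It can also be argued that the scope suits the decision. Section 10.2 asks about the rifabutin and LPV/r doses, and section 9.5.1 provides for adjusting only those drugs. That is a fair reason to keep a study-provided count. It does not explain applying one limit to different drug sets while describing the result as a test of the regimen.

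Finally, the reviews are partly discretionary. Loss to follow-up before day 28 is a failure in every arm (9.6.1), and SAP 4.1 tabulates Grade 2 or higher events without attribution. The first leaves the asymmetry unchanged, and the second has no pass/fail rule.

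**Conclusion.** The asymmetry is in the text and needs no assumption: the rifamycin is inside the counted set in Arms A and C and outside it in Arm B. It follows that Arm B's chance of passing is higher than it would be if rifampin-only events counted. The size rests on assumed, independent rates: 0.867 against 0.796 to 0.456 on criterion 1, for 10% LPV/r-attributed and 2% to 10% rifampin-only events. It shrinks as more mixed-cause events are scored as possibly related to LPV/r. No advantage over A or C is established.

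The point falls short of an essential correction. SAP 1.6 states that accrual period 2 will not open, so the criteria no longer gate enrolment, and the second review in 9.5.1 weighs the nature of the events. It still matters because SAP 4.1 and 4.2 tabulate the criteria by arm and SAP section 6 will report whether they were acceptable. The differing attribution levels in the SAP and the conflicting statements on rifampin's supply are defects in their own right.

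**What to change.** **Protocol.** In 9.2.1.3, 9.2.1.4, 9.5.1 and 9.6.1, define one counted set for all arms: LPV/r, RTV, RAL or the assigned rifamycin, whoever supplies it. Reconcile 6.2.2 and 7.2.5 with the Schema, 3.0, 5.1.1 and 5.3.1 on whether rifampin is study-provided.

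**SAP.** Keep the prespecified study-provided-only count. The core team reviewed data unblinded each week (9.5.1), and the early assessment went to the SMC in January 2016 (SAP 1.4). Replacing the criterion in an October 2016 SAP would be a change made with knowledge of the data. In 4.1 and 4.2, report the rifampin-inclusive count and its pass/fail result beside the prespecified one for both criteria, and state any differing verdict in section 6. Use one attribution level in 1.5.2 and 4.1.

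**Cost.** Wording changes, plus a review of Arm B events for attribution to rifampin. Grade 3 or higher events and TB drug discontinuations are already recorded in every arm (6.3.5, 6.3.9), so no new data collection is needed. Arm B may look less favourable.
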